7. VARIABLES

The following parameters will be collected at **visit 1** (= index date 1) of all registered patients:

1. Patient demographics:
 - Year of birth
 - Gender
 - Height, weight, BMI (will be calculated from height and weight)
2. Date of first diagnosis of HF
3. Etiology of heart failure
 - Coronary artery disease
 - Hypertension
 - Valve disease
 - Cardiomyopathy
 - Congenital heart disease
 - Drug induced
 - Infective
 - Storage disorders
 - Diabetes
 - Obesity
 - Other
4. Clinical parameters relevant for HF (last available value and date when it was collected) as valid at baseline and performed during clinical routine:
 - LVEF [%]
 - Current NYHA Class [I-IV] according to treating physician
 - Electrocardiogram (ECG) (normal/abnormal-not clinically significant/abnormal-clinical significant and QTc interval)
 - Heart rate [bpm]
 - Blood pressure (systolic, diastolic) [mmHg]
 - Laboratory diagnostic according to clinical routine (last available value and date when it was collected):
 - BNP (B-type natriuretic peptide) and/or pro-BNP (N-terminal pro-B-type natriuretic peptide)
 - Lipids (cholesterol, HDL, LDL)
 - Blood urea nitrogen (BUN)
 - Serum creatinine
 - Sodium, potassium
 - Complete blood count
 - 6-min-walking test according to clinical routine
5. Alcohol consumption (none, from time to time, regular) and smoking status (non-smoker, previous smoker, current smoker)
6. Concomitant diseases / Comorbidities
 - Disease according to ICD-10 (diabetes, hypertension, coronary artery)

BOEHRINGER INGELHEIM Group of Companies

Title: Statistical and Epidemiological Analysis Plan (SEAP)
for Observational and Non-Interventional Studies
(ONIS) Template

Page 9 of 19

Name: BI-VQD-12133_90-118_AD-20

Version 3.0

disease, infarction, chronic kidney disease, atrial fibrillation, cancer, other)

- Date of first diagnosis

7. Previous HF hospitalizations within the last 6 months
8. HF related medication used in the last 6 months
 - Medication
 - Indication
 - Application
 - Dose
 - Start date, end date, continuing
9. Current HF related and other relevant concomitant medication
 - Medication
 - Indication
 - Application
 - Dose
 - Start date, end date, continuing
10. Newly prescribed treatment regime:
 - Date of prescription
 - Medication (empagliflozin and / or other drug)
 - Reason, if no prescription of empagliflozin
11. Patient reported outcomes:
 - KCCQ (23 items) completed by patients during the visit

The following parameters will be collected at routine **visit 2** [= index date 2: 24 weeks (± 2 weeks) after index date 1] only of registered patients treated with empagliflozin:

1. Weight, BMI (will be calculated from height and weight)
2. Clinical parameters relevant for HF performed during clinical routine (last available value and date when it was collected):
 - LVEF
 - Current NYHA Class according to treating physician
 - Electrocardiogram (ECG)
 - Heart rate
 - Blood pressure (systolic, diastolic)
 - Laboratory diagnostic according to clinical routine (last available value and date when it was collected):
 - BNP (B-type natriuretic peptide) and/or pro-BNP (N-terminal pro-B-type natriuretic peptide)
 - Lipids (cholesterol, HDL, LDL)
 - Blood urea nitrogen (BUN)
 - Serum creatinine
 - Sodium, potassium
 - Complete blood count

- 6-min-walking test according to clinical routine
- 3. Current HF related or other relevant concomitant medication
- 4. HF drug(s) prescribed at visit 2
- 5. Patient reported outcomes:
 - KCCQ (23 items) completed by patients during the visit
- 6. Safety: ADRs (serious and non-serious), fatal adverse events (AEs), pregnancies, HF related hospitalizations
- 7. Discontinuation of treatment with empagliflozin during study period (yes/no)
 - If yes: date of discontinuation, reason (if applicable)
- 8. Continuation or discontinuation of treatment with empagliflozin after study period (yes/no)
 - In case of discontinuation: date of discontinuation, reason (if applicable)

The following variables have to be calculated:

BMI: Body weight [kg] / (Height [m])²

Kansas City Cardiomyopathy Questionnaire (KCCQ-23):

The Kansas City Cardiomyopathy Questionnaire Scoring Instructions

There are 10 summary scores within the KCCQ, which are calculated as follows:

1. Physical Limitation

- Code responses to each of Questions 1a-f as follows:

Extremely limited = 1
Quite a bit limited = 2
Moderately limited = 3
Slightly limited = 4
Not at all limited = 5

Limited for other reasons or did not do = <missing value>

- If at least three of Questions 1a-f are not missing, then compute

Physical Limitation Score = $100 * [(mean\ of\ Questions\ 1a-f\ actually\ answered) - 1] / 4$
(see footnote at end of this section for explanation of meaning of "actually answered")

2. Symptom Stability

- Code the response to Question 2 as follows:

Much worse = 1
Slightly worse = 2
Not changed = 3
Slightly better = 4
Much better = 5
I've had no symptoms over the last 2 weeks = 3

- If Question 2 is not missing, then compute

Symptom Stability Score = $100 * [(Question\ 2) - 1] / 4$

3. Symptom Frequency

- Code responses to Questions 3, 5, 7 and 9 as follows:

BOEHRINGER INGELHEIM Group of Companies

Title: Statistical and Epidemiological Analysis Plan (SEAP)
for Observational and Non-Interventional Studies
(ONIS) Template

Page 11 of 19

Name: BI-VQD-12133_90-118_AD-20

Version 3.0

Question 3

Every morning = 1
3 or more times a week but not every day = 2
1-2 times a week = 3
Less than once a week = 4
Never over the past 2 weeks = 5

Questions 5 and 7

All of the time = 1
Several times a day = 2
At least once a day = 3
3 or more times a week but not every day = 4
1-2 times a week = 5
Less than once a week = 6
Never over the past 2 weeks = 7

Question 9

Every night = 1
3 or more times a week but not every day = 2
1-2 times a week = 3
Less than once a week = 4
Never over the past 2 weeks = 5

- If at least two of Questions 3, 5, 7 and 9 are not missing, then compute:

$S3 = [(Question 3) - 1]/4$
 $S5 = [(Question 5) - 1]/6$
 $S7 = [(Question 7) - 1]/6$
 $S9 = [(Question 9) - 1]/4$

Symptom Frequency Score = $100 * (\text{mean of } S3, S5, S7 \text{ and } S9)$

4. Symptom Burden

- Code responses to each of Questions 4, 6 and 8 as follows:

Extremely bothersome = 1
Quite a bit bothersome = 2
Moderately bothersome = 3
Slightly bothersome = 4
Not at all bothersome = 5
I've had no swelling/fatigue/shortness of breath = 5

- If at least one of Questions 4, 6 and 8 is not missing, then compute

Symptom Burden Score = $100 * [(\text{mean of Questions 4, 6 and 8 actually answered}) - 1]/4$

5. Total Symptom Score

= mean of the following available summary scores:

Symptom Frequency Score

Symptom Burden Score

6. Self-Efficacy

- Code responses to Questions 10 and 11 as follows:

Question 10

Not at all sure = 1
Not very sure = 2

BOEHRINGER INGELHEIM Group of Companies

Title: Statistical and Epidemiological Analysis Plan (SEAP)
for Observational and Non-Interventional Studies
(ONIS) Template

Page 12 of 19

Name: BI-VQD-12133_90-118_AD-20

Version 3.0

Somewhat sure = 3

Mostly sure = 4

Completely sure = 5

Question 11

Do not understand at all = 1

Do not understand very well = 2

Somewhat understand = 3

Mostly understand = 4

Completely understand = 5

- If at least one of Questions 10 and 11 is not missing, then compute

Self-Efficacy Score = $100 * [(\text{mean of Questions 10 and 11 actually answered}) - 1] / 4$

7. Quality of Life

- Code responses to Questions 12, 13 and 14 as follows:

Question 12

It has extremely limited my enjoyment of life = 1

It has limited my enjoyment of life quite a bit = 2

It has moderately limited my enjoyment of life = 3

It has slightly limited my enjoyment of life = 4

It has not limited my enjoyment of life at all = 5

Question 13

Not at all satisfied = 1

Mostly dissatisfied = 2

Somewhat satisfied = 3

Mostly satisfied = 4

Completely satisfied = 5

Question 14

I felt that way all of the time = 1

I felt that way most of the time = 2

I occasionally felt that way = 3

I rarely felt that way = 4

I never felt that way = 5

- If at least one of Questions 12, 13 and 14 is not missing, then compute

Quality of Life Score = $100 * [(\text{mean of Questions 12, 13 and 14 actually answered}) - 1] / 4$

8. Social Limitation

- Code responses to each of Questions 15a-d as follows:

Severely limited = 1

Limited quite a bit = 2

Moderately limited = 3

Slightly limited = 4

Did not limit at all = 5

Does not apply or did not do for other reasons = <missing value>

- If at least two of Questions 15a-d are not missing, then compute

Social Limitation Score = $100 * [(\text{mean of Questions 15a-d actually answered}) - 1] / 4$

9. Overall Summary Score

= mean of the following available summary scores:

Physical Limitation Score
Total Symptom Score
Quality of Life Score
Social Limitation Score

10. Clinical Summary Score

= mean of the following available summary scores:

Physical Limitation Score
Total Symptom Score

Footnote: references to “**means of questions actually answered**” imply the following.

If there are n questions in a scale, and the subject must answer m to score the scale, but the subject

answers only $n-i$, where $n-i \geq m$, calculate the **mean of those questions** as

(sum of the responses to those $n-i$ questions) / ($n-i$)

not

(sum of the responses to those $n-i$ questions) / n

Left ventricular ejection fraction (LVEF): HF can be classified into 3 subtypes with different underlying aetiologies:

1. HF with reduced ejection fraction (HFrEF) (LVEF $\leq 40\%$),
2. HF with preserved ejection fraction (HFpEF) (LVEF $\geq 50\%$) and
3. HF with mildly reduced LV systolic function (HFmrEF) (LVEF = 41-49%).

Time to discontinuation of empagliflozin treatment: Time to discontinuation of empagliflozin treatment will be analyzed descriptive using Kaplan-Meier methods. For patients who discontinued empagliflozin treatment it will be derived as date of end of treatment - date of start of treatment +1, patients still on treatment will be censored with date of last contact.

7.1 EXPOSURES

The drug of interest is Jardiance® with the active ingredient empagliflozin. Within this study, there are two HF patient cohorts: patients receiving first prescription of empagliflozin and those who have been prescribed a drug with a different mechanism of action for the treatment of HF, i.e. non-SGLT2i.

During this study, it is planned to observe for each patient who receives a first prescription of empagliflozin a treatment period of approximately 24 weeks. Patients not treated with empagliflozin will not be observed further after visit 1.

The recommended daily dose of empagliflozin for treatment of heart failure is 10 mg once daily.

7.2 OUTCOMES

[figure not shown]
7.2.1 Primary outcomes

Change of the Kansas City Cardiomyopathy Questionnaire (KCCQ) scores [clinical summary score (CSS), total symptom score (TSS), overall summary score (OSS)] from index date 1

(baseline) to index date 2 (24 weeks after index date 1) in patients newly treated with empagliflozin according to routine practice.

7.2.2 Secondary outcomes

- Change of the New York Heart Association (NYHA) Class from index date 1 to index date 2 (24 weeks after index date 1) in patients newly treated with empagliflozin.
- Real-world patterns of patient characteristics, clinical disease presentation and therapeutic regimen chosen in participants with chronic HF as well as of patient reported outcome at visit 1.

7.3 COVARIATES

Demographics and disease characteristics will be used to define subgroups of interest.

8. DATA SOURCES

Medical records collected through routine clinical care will be used to assess the inclusion/exclusion criteria of patients as well as for patient demographics, current HF medication, concomitant diseases, and concomitant medication, as well as for the health data of the patient at visit 2.

The KCCQ will be provided as paper version by the treating physician or trained site staff to the patient to be filled out in writing at visit 1 (all patients) and visit 2 (patients with initial empagliflozin treatment only).

9. DATA MANAGEMENT AND SOFTWARE / TOOLS

9.1 SOFTWARE/TOOLS

SAS® Version 9.4 or higher will be used for all analyses.

9.2 HANDLING OF MISSING VALUES

All patient discontinuations will be documented and the reason for discontinuation will be recorded.

In general, it is not planned to impute missing values. Exceptions are detailed in the subsequent subsections.

9.3 HANDLING OF INCONSISTENCIES IN DATA AND OUTLIERS

Not planned.

10. DATA ANALYSIS

Full analysis set (FAS): All registered patients who gave informed consent.

All data captured at visit 1 will be analysed for FAS.

Primary endpoint set (PES): All patients, who received at least one dose of empagliflozin for HF and have filled in KCCQ at time points index date 1 and 24 week follow-up visit. The primary endpoint will be analysed for PES.

Safety set (SAF): All patients of FAS who received empagliflozin at least once. SAF will be used for safety and further analyses.

For continuous variables number of values, mean, standard deviation, minimum, 5th percentile, 25th percentile, median 75th percentile, 95th percentile, maximum and number of missing values will be presented. For categorical variables the number and percentage with a category for missing will be given.

Percentages will be rounded to two decimal places.

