9.3.2 Outcomes

This NIS will describe contemporary, real-world patterns of patient characteristics, clinical disease presentation, and therapeutic regimen chosen in participants with chronic HF in CEE countries. Additionally, PRO is assessed by use of the disease specific KCCQ. These data will be collected at visit 1 of all registered patients.

The primary objective is to document and analyze QoL data from patients with HF receiving first treatment with empagliflozin in daily routine care. For this approach, the disease specific KCCQ is used to examine changes from index date 1 to index date 2 (= 24 weeks after study index date 1) in these patients. The primary outcome will be evaluated on patients receiving initial prescription of empagliflozin at visit 1 and who have filled in the KCCQ at visit 1 and visit 2.

[figure not shown]
The primary and secondary outcomes do not touch any safety questions.

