9.7 DATA ANALYSIS

Statistical analysis will be performed by [REDACTED]).

The statistical analysis plan (SAP) for the study is summarized below. Full details of the statistical analysis will be documented in the SAP, which will be finalized before the end of data collection.

In general, all analyses will be carried out by using descriptive and exploratory statistical methods including exploratory confidence intervals and p-values. For the analyses SAS® software version 9.4 or higher will be used.

All data captured at visit 1 will be analyzed on all registered patients [Full analysis set (FAS)]. All patients who have received at least one dose of empagliflozin for HF and have filled in KCCQ at time points 'index date 1' and 'index date 2 (= week 24 after index date 1)' will be included in the 'primary endpoint set' which will be used for primary endpoint analysis.

Safety set: All patients who received empagliflozin at least once will be used for safety and further analyses.

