5. RESEARCH QUESTION AND OBJECTIVE

5.1 PRIMARY OBJECTIVE

The primary objective of this observational study is to describe the change of the clinical summary score (CSS), total symptom score (TSS), and overall summary score (OSS) of the Kansas City Cardiomyopathy Questionnaire (KCCQ) from baseline to 24 weeks in patients with chronic HF newly treated with empagliflozin according to routine practice.

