10.1 MAIN ANALYSIS

Analysis of the primary outcome

- Change of each of the Kansas City Cardiomyopathy Questionnaire (KCCQ) scores [clinical summary score (CSS), total symptom score (TSS), overall summary score (OSS)] from index date 1 to index date 2 (= 24 weeks after index date 1) in patients newly treated with empagliflozin according to routine practice

will be performed according to the analysis manual for the KCCQ. Changes in the KCCQ scores will be calculated for each patient. Results will be presented as N, mean, standard deviation, median, minimum and maximum values as well as number of missings as extra column. A change of 5 points of OSS will be considered as clinically meaningful.

In addition, change from index date 1 in clinical summary score for HF symptoms and physical limitations domains of the KCCQ at week 24 will be evaluated by subgroups based on age at index date 1 (<50/50-<65/65-<75/≥75 years as well as <65/≥65 years), gender, country, baseline LVEF (HFrEF, HFmrEF HFpEF), and status of diabetes mellitus at visit 1. All recorded data for efficacy up to week 24 will be included.

For analysis of the secondary outcome

- Change of the New York Heart Association (NYHA) Class from index date 1 to index date 2 (= 24 weeks after index date 1) in patients newly treated with empagliflozin tabulation of relative and absolute frequencies will be presented as well as a shift table.

For the analysis of the secondary outcome

- Capture of real-world patterns of patient characteristics, clinical disease presentation and therapeutic regimen chosen in participants with chronic HF as well as of patient reported outcome at visit 1

tabulations of relative and absolute frequencies will be presented. Comparison of data at visit 1 between patients receiving empagliflozin or not for treatment of HF will be performed by Chi- quadrat-test or Mann-Whitney-U-test or Student t-Test.

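### The primary KCCQ change is estimated only in treated patients with both questionnaires, and no sensitivity analysis of that restriction is visible

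*SAP*

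**What the plan says.** SAP 5.1 sets out to describe the change in three KCCQ scores "from baseline to 24 weeks in patients with chronic HF newly treated with empagliflozin according to routine practice". Protocol section 8 gives the same objective.

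The analysis population is narrower. Protocol 9.3.2 evaluates the primary outcome in patients first prescribed empagliflozin at visit 1 "who have filled in the KCCQ at visit 1 and visit 2". Under protocol 9.7, treated patients with both questionnaires "will be included in the 'primary endpoint set' which will be used for primary endpoint analysis". SAP section 10 repeats this for patients who took the drug at least once: "and have filled in KCCQ at time points index date 1 and 24 week follow-up visit. The primary endpoint will be analysed for PES".

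On missing data, SAP 9.2 says "In general, it is not planned to impute missing values" and points to exceptions in later subsections. None is visible for an absent week-24 KCCQ. The same section says "All patient discontinuations will be documented and the reason for discontinuation will be recorded". SAP 10.1 reports the change with summary statistics "as well as number of missings as extra column", and names 5 points on the overall summary score (OSS) as the meaningful change.

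**The concern.** The objective speaks of everyone newly treated, but the estimate comes from those who returned and filled in a second form. The two agree only if the patients who drop out of view changed, on average, as much as those who stayed. Nothing visible examines this.

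It matters here for three reasons. The result is a within-patient change, and the non-empagliflozin cohort is not followed after visit 1, so no comparator shares the same loss. The KCCQ is scheduled only at visits 1 and 2, so no interim score exists for a patient who misses visit 2. And the study is justified by how well its patients represent routine practice (protocol sections 7 and 9.5). Its limitations section (9.9) discusses selection of sites and selection at enrolment, but not loss between the visits.

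**Working it through.** **What the visible text already yields.**

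- The missing column in the primary table, if run on the PES, counts only forms that were filled in but cannot be scored. Patients who never returned a form are outside the set.
- The KCCQ scoring rules in SAP section 7 deal with missing items, not a missing questionnaire.
- SAP sections 10 and 10.1 require visit-1 data, including the KCCQ, to be summarised by cohort with numbers of values and of missing values. Empagliflozin patients with a scorable baseline KCCQ, minus the PES, therefore give an approximate non-return total. Never-dosed patients and unscorable forms blur it slightly.
- The NYHA shift table, if run on the safety set (SAF; the set is not stated), may show missing visit-2 class by baseline class.
- The Kaplan-Meier analysis in SAP section 7 concerns stopping the drug, not failing to return a form.
- The visit-1 tests compare empagliflozin with non-empagliflozin patients, not PES with treated non-PES patients.

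So an approximate total can be had, but no reasons for non-return and no adjusted estimate.

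**Size of the possible shift.** Inputs from the documents: about 3300 empagliflozin starters, 4600 patients in total and a minimum of 100 per country (protocol 9.2.1 and 9.5), and the 5-point OSS benchmark (SAP 10.1). The plan states no figure for loss or precision, so there is nothing to reproduce. Assumed: share missing p, gap g and SD of change.

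Let p be the share of surviving starters with a baseline KCCQ who lack the week-24 form, and g the completer mean change minus the non-returner mean change. The mean over all of them is (1 − p) × completer mean + p × (completer mean − g) = completer mean − p × g. The overstatement is therefore p × g.

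For scale, the 95% half-width is 1.96 × SD / √(3300 × (1 − p)). This ignores site clustering and treats all 3300 as surviving with a baseline form. The product p × g does not depend on that simplification.

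| p | Completers | p × g, g = 5 | p × g, g = 10 | Half-width, SD 20 (SD 15 to 25) | Mean in all, if completer mean is 5 |
|---|---|---|---|---|---|
| 5% | 3135 | 0.25 | 0.5 | 0.70 (0.53 to 0.88) | 4.75 to 4.5 |
| 10% | 2970 | 0.5 | 1.0 | 0.72 (0.54 to 0.90) | 4.5 to 4.0 |
| 20% | 2640 | 1.0 | 2.0 | 0.76 (0.57 to 0.95) | 4.0 to 3.0 |
| 30% | 2310 | 1.5 | 3.0 | 0.82 (0.61 to 1.02) | 3.5 to 2.0 |

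At SD 20, the gap at which the shift equals the half-width (half-width / p) is 14.0, 7.2, 3.8 and 2.7 points. A large sample therefore does not protect against this shift.

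**Country level.** With the overall cohort split, the minimum of 100 patients gives 100 × 3300 / 4600 ≈ 72 starters. At 20% loss about 57 remain, and the half-width at SD 20 is 5.2 points, against a shift of 1.0 to 2.0. Random error dominates there, so the point concerns the overall mean.

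**The case against.** The strongest reply is that the population is declared. Protocol and SAP agree, the study is descriptive and free of hypotheses, and a completer mean labelled as such is a correct summary of completers. That stands: a reader might infer a conflict between the documents or an invalid analysis, and neither is there.

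Second, the shift rests entirely on assumed inputs. This also stands. A reader might infer that the published change will be too favourable, but the documents give no evidence on how non-returners fare. Early deaths should be few, because a life expectancy of 12 months or less is an exclusion. Nor is the half-width a decisive yardstick. Protocol 9.7 foresees "exploratory statistical methods including exploratory confidence intervals and p-values", but SAP 10.1 lists no interval for this outcome, and with over 2300 patients even a small shift exceeds it. Against the 5-point benchmark, the shift at 5 to 10% loss is at most 1.0.

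Third, the plan is not silent on non-return: the total can be approximated and reasons for discontinuation are recorded. This narrows the gap without closing it.

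Fourth, absence cannot be confirmed. Section numbering passes over SAP 10.2 and protocol 9.7.2, some figures are not shown, and the table shells are a separate document. The point is therefore limited to the visible text.

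**Conclusion.** The point holds as a cheap improvement. The primary set can give a biased mean for the stated objective, and no visible analysis tests for it. Under assumed gaps of 5 to 10 points, the overstatement is 0.25 to 1.0 points at 5 to 10% loss and 1.0 to 3.0 points at 20 to 30% loss. That is small against the 5-point benchmark at low loss and up to 60% of it (3.0 / 5) at the top of the range. SAP 10.1 does not say whether the benchmark applies to a single patient or to the group mean; the last column of the table takes it as a group mean. If non-returners did as well as completers the shift is nil, and if they did better it reverses.

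**What to change.** Keep the PES analysis as primary and add to SAP 10.1:

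- **(a) One sensitivity analysis of the KCCQ change** in SAF patients with a baseline KCCQ, by multiple imputation or inverse-probability weighting on visit-1 variables: KCCQ, NYHA class, LVEF class, age, sex, diabetes and country. Report deaths separately and do not impute them, so that the target is the change among survivors. Because baseline variables correct only the part of the bias that they explain, add a simple delta range: subtract p × delta from the adjusted mean, for example for delta from 0 to 10 points, the upper end of the gaps assumed above.
- **(b) In support,** the number of these patients without a week-24 KCCQ, by reason where recorded and with unknown allowed, and their baseline characteristics beside those of the PES.

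No new data field is needed. Visit-1 variables are collected on everyone, and fatal events are collected from consent to the end of the study. No visible field records why a questionnaire was not completed, so unknown may be common. Empagliflozin discontinuation and HF hospitalization are listed at visit 2 and may be missing for non-returners, so the analysis should not depend on them.

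The cost is SAP wording, some extra programming, a missing-at-random assumption that cannot be tested (eased by the delta range), and possibly a less favourable figure. If SAP 10.2 or the shells already contain any of this, a cross-reference is enough.
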